2.4 Determination of sample size

As detailed in [Section 4.4](#), this study will consist of 2 stages, with a formal interim analysis at the end of Stage 1.

Based on historical data, the mean difference in adjusted changes from Baseline of MG-ADL at Day 43, between rozanolixizumab and placebo, is assumed to be 1.5 to 2.0 and the standard deviation is assumed to be 3.5 to 4. A difference of >1.5 could be judged to be clinically meaningful.

It is proposed that the interim analysis will be conducted when approximately 90 eligible study participants have been treated and are evaluable for the primary endpoint, i.e., approximately 30 study participants per dose group in Stage 1. If the study is not stopped for futility after Stage 1, the sample size will be increased, subject to a maximum cap, to provide an overall conditional power target of 90% based on the observed effect size in Stage 1. For each dose that is not futile, the comparison-wise conditional power will be calculated which is the probability of, given the observed data, to achieve a significant result for the completed trial if only the considered treatment is selected. If two doses are selected, then the conditional power associated with the higher treatment effect will be used to determine the stage 2 sample size. Conditional power will be calculated as described in formula 7.2 of Wassmer and Brannath (2016). Similarly, the stage 2 sample size required to achieve a target conditional power of 90% will be calculated using a formula derived from formula 7.4 of Wassmer and Brannath (2016) as follows:

$$\text{Second stage sample size per arm} = 2 * SD^2 * [\phi^{-1}(TP) + \phi^{-1}(1-CRP)]^2 / \Delta^2$$

Where,

SD = pooled standard deviation from the stage 1 statistical model using all dose groups

TP = target conditional power = 0.9

CRP = Conditional rejection probability at stage 1 for the dose group being considered

Delta = assumed true treatment effect for second stage data

If two doses are considered for stage 2 then the above formula will be applied with the conditional error divided by two, to account for multiplicity. Depending upon the selection of one, or two, of the doses after Stage 1, a further 60 to up to a maximum of 150 eligible study participants will be randomized in Stage 2 of the study. Thus, the total sample size of the study could range between 150 and 240 study participants if the study is not futile at Stage 1.

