8.2.2 Primary analysis of the primary efficacy endpoint

The primary analysis is based on the RS under the hypothetical & treatment policy strategy (see details in [Section 8.1](#)). Any missing MG-ADL scores (including missing data after the intercurrent events) will be handled based on maximum likelihood estimation method under MAR assumption.

A stage-wise MMRM with treatment group, Baseline MG-ADL score, region, stratification factor(s) including MuSK(+/-) and /or AChR(+/-), and treatment group by day (interaction term) as fixed factors and study participant as a random effect. The MMRM will include Days 8, 15, 22, 29, 36 and 43.

The model will utilize an unstructured covariance pattern for the repeated measures. If the model does not converge using the unstructured pattern, then an autoregressive covariance structure

will be used. The Kenward-Roger approximation will be used to estimate the denominator degrees of freedom.

For each stage, the least squares means (LSMs) of each treatment group, and the least squares mean differences (LSMDs) between each dose group and placebo will be reported for Day 43 (Visit 10), along with the corresponding 2-sided 97.5% CIs and p-values.

The study follows a 2-stage group sequential adaptive design using combination test (Lehmacher and Wassmer, 1999) based on the inverse-normal method of combining independent stagewise p-values (Hedges and Olkin, 1985)

The analysis takes into account that the study is a 2-stage group sequential adaptive design assuming equal weighting of each stage, with weights = $1/\sqrt{2}$:

- Stage 1 – Cohort up to the formal IA
- Stage 2 – Cohort post-IA

The following sequential test statistic will be used to test the global null hypothesis at the end of stage 2:

$$T = \sum_{i=1}^2 w_i \phi^{-1}(1 - p_i)$$

Where subscript $i = 1, 2$ represents the stage, p_i represents the appropriate multiplicity adjusted p-value at stage i (for example at stage 1, $p_1 = \min(2 * p_{\min}, 1)$ where p_{\min} is the minimum of the two nominal p-values), the weights $w_{ki} = 1/\sqrt{2}$ satisfy $\sum_{i=1}^2 w_{ki}^2 = 1$ and ϕ^{-1} is the inverse cumulative standard normal distribution function. The test statistic T and $z = \phi^{-1}(1 - p_i)$ have a standard normal distribution, (Lehmacher and Wassmer, 1999).

The combined p-value (2-sided) for the 2 stages, which tests the global null hypothesis, can be calculated by:

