$$p = 2 * \{1 - \Phi[\frac{1}{\sqrt{2}} \{\phi^{-1}(1 - p_1) + \phi^{-1}(1 - p_2)\}]\}$$

At the IA one p-value will be computed for each pairwise comparison. Assuming that the trial is not stopped for futility at IA, at the end of the trial the t-test statistics computed at each stage will be used following the p-value combination test method to derive the combined p-value for evaluation of primary efficacy endpoint. Overall statistical significance will be concluded if the combined p-value (2-sided) described above is less than 0.05. For each dose group, statistical significance will be determined in a similar way but using a closed test procedure. Formally, this will be computed as the p-value corresponding to the minimum adjusted Z-statistic of all hypotheses involving the particular dose group being considered. However, if one treatment arm with the largest test statistic is selected for the second stage, the rejection of the global hypothesis implies the rejection of the hypothesis related to the selected hypothesis. The pre-determined alpha value for secondary endpoint testing is specified in [Section 4.6](#).

The analysis will be conducted using SAS and RPACT which also produces the combined effect estimates together with multiplicity adjusted 95% CIs. The stagewise inputs for Rfact will be the model Least squares means, standard errors, sample size per group and degrees of freedom (for estimation of the common standard deviation).

The overall confidence intervals at stage 2 are computed separately for each treatment arm that was selected for stage 2. By use of the Inverse-Normal combination function together with the critical value $Z_{\alpha/2}$, the lower bound of the 2-sided 95% repeated confidence interval for a given treatment arm is found as the smallest value for which the multiplicity-adjusted combination test yields non-rejection at two-sided $\alpha=5\%$. The upper bound of the confidence interval will be found analogously.

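### The inputs listed for the combined estimate and CI omit the LS mean difference and its SE, so the interval need not invert the primary test

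*SAP*

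**What the plan says.** SAP 8.2.2 distinguishes two kinds of model output. For each stage it reports "the least squares means (LSMs) of each treatment group, and the least squares mean differences (LSMDs) between each dose group and placebo". The confirmatory decision uses the second kind: "at the end of the trial the t-test statistics computed at each stage will be used following the p-value combination test method", with "assuming equal weighting of each stage" and the rule that "Overall statistical significance will be concluded if the combined p-value (2-sided) described above is less than 0.05". Protocol 9.4.1 likewise derives the stage-wise p-values from t statistics for each dose.

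For estimation, SAP 8.2.2 names SAS and RPACT, "which also produces the combined effect estimates together with multiplicity adjusted 95% CIs". The RPACT inputs are described as "The stagewise inputs for Rfact will be the model Least squares means, standard errors, sample size per group and degrees of freedom", with a parenthesis saying that they serve to estimate the common standard deviation. The last paragraph of the section defines the lower confidence bound by test inversion, as "the smallest value for which the multiplicity-adjusted combination test yields non-rejection at two-sided" 5%.

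The section does not say how the LS means are weighted over region and antibody status. It contains no check that the RPACT inputs reproduce the MMRM p-values.

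**The concern.** Elsewhere the SAP names differences when it means them. Section 8.2.3.2 pools standard errors of both LSMs and LSMDs, and 8.4.3 carries forward the log-hazard ratio with its own standard error. The RPACT sentence names only LS means and sits beside a per-group sample size, so the natural reading is arm-level standard errors.

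An arm LS mean is a prediction at a chosen covariate profile. Its SE includes the uncertainty of the region, antibody and baseline coefficients. That part is common to all arms and drops out of a treatment difference. An SD built from arm-level SEs keeps it in. The p-value and the CI for the primary endpoint would then rest on different standard errors, although the SAP defines one as the inversion of the other. The same approach is reused in several sensitivity and supplementary analyses of the primary endpoint and for the five continuous secondary endpoints (8.3.2 to 8.3.6).

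**Working it through.** **1. The plan's own figures.** The SAP states no SE or CI for this point, so the design was checked against Table 2-1. The inputs were "approximately 30 study participants per dose group in Stage 1", 30 to 50 per arm in Stage 2, the 1-point dose-selection rule, the SAP 2.4 sample size formula, equal weights, the Bonferroni closed test and one-sided 0.025. Stated against simulated power:

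- scenario 1: 0.020 / 0.020
- scenario 4: 0.750 / 0.763
- scenario 13: 0.792 / 0.803

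All eight scenarios tried agreed within 2 points.

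**2. Algebra.** For one dose and placebo, Var(LSMD) = V_dose + V_placebo − 2·Cov. The listed inputs contain no covariance. An SD from arm-level inputs is SD = SE_LSM·√n. The implied SE of the difference is SD·√(1/n_dose + 1/n_placebo), which is √2·SE_LSM for equal arms. It is too large whenever Cov is positive.

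**3. Mechanism in the simplest case.** This is a single-visit ANCOVA with SD 3.5, 30 per arm and three arms. The shares are assumptions, because the documents give none: MuSK+ 10%, regions 3/57/33/7%.

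- Equal weighting over factor levels: median arm SE 1.04, so the implied SE is about √2 × 1.04 = 1.47. The true SE of the difference is 0.92. The median simulated ratio is 1.58.
- Equal weighting with even regions: median ratio 1.26.
- Observed margins: arm SE 0.648, so the implied SE is √2 × 0.648 = 0.916 against a true 0.926. The ratio is 0.99.

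**4. The planned model.** SAP 8.2.2 specifies an MMRM over Days 8 to 43. Baseline, region and antibody status enter as main effects without covariate-by-day terms, so all six visits help to estimate them and the shared part shrinks. The assumptions are regions 35/50/8/7%, MuSK+ 10%, 30 per arm and assumed within-patient covariances.

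| Model and weighting | Implied SE / model SE of difference |
|---|---|
| Single-visit ANCOVA, equal weights | 1.41 |
| Six-visit MMRM, equal weights, constant SD 3.5 | 1.27 to 1.34 |
| Six-visit MMRM, equal weights, SD rising from 2.0 to 3.5 | 1.14 |
| Observed margins | 0.99 to 1.00 |

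CI half-width scales with this ratio, so equal weighting makes the interval roughly 14% to 34% too wide under the planned model.

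**5. Sensitivity to the assumed shares.** In the single-visit case with the 35/50/8/7% mix, the ratio is 1.25 at 20% MuSK+ and 1.69 at 5%. With even regions it runs from 1.09 to 1.59. The MMRM figures would also move with these shares.

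**6. After the repair.** With SD = SE(LSMD)/√(1/n_dose + 1/n_placebo), the implied SE is SD·√(1/n_dose + 1/n_placebo) = SE(LSMD), and the ratio is 1.00.

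**The case against.** The strongest reply is that the SAP never says whose standard errors are passed. If SE(LSMD) was meant, the problem disappears. SAP 2.4 already speaks of a pooled SD from the stage 1 model, and the documents do not describe how RPACT turns its inputs into an interval. This stands as a limit: the concern rests on the natural reading of one sentence, not on an explicit instruction. The sentence still needs correcting, because a programmer following it literally would pass arm-level values.

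A second reply is that the test-inversion definition governs, so an arm-level implementation would breach the SAP. That is true, but it shows that two statements in the same section may not be compatible. It does not settle which one is coded.

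A third reply concerns size. A reader might take the single-visit ratio of about 1.4 as the trial's figure. The planned MMRM does not support that, and observed margins remove the effect.

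A reader might also ask that the CI exclude zero exactly when the closed test rejects. The documents do not support this as a check. Each dose is tested by a closed procedure, while the interval is multiplicity-adjusted. If that adjustment is single-step Bonferroni, then even with correct SEs the closed test rejects while the interval covers zero in about 13.6% of trials (effect 1.5, SD 3.5, 30 per arm per stage, both doses kept). Such a mismatch would not by itself show a wrong SE.

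**Conclusion.** The concern holds as a defect in the stated inputs for the primary interval. On the natural reading, the combined CI is not guaranteed to invert the MMRM-based combination test. With equal weighting, the implied SE is about 1.1 to 1.35 times the correct one under the planned MMRM. With observed margins it is about 1.0. The range rests on assumed region shares, MuSK prevalence and covariance patterns, and the SAP leaves the weighting open.

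Three stronger inferences are not supported:

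- **Inflated type I error.** The decision uses the stage-wise t-tests, which do not depend on the RPACT inputs, and the error widens the interval.
- **Loss of power.** This would follow only if RPACT p-values built on the wider SE replaced those from the t-tests, which SAP 8.2.2 does not say.
- **A CI covering zero in a large share of trials that reject.** Single-visit simulations with equal weighting give 43% (uneven regions) and 26% (even regions) at effect 1.5 and SD 3.5. They do not use the planned six-visit model, so they are not estimates for this trial.

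What is at stake is the precision reported for the primary and continuous secondary effects, and its coherence with the tests.

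**What to change.** Amend the RPACT sentence in SAP 8.2.2 in one of two ways:

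- State that, for each dose and stage, the SD passed is SE(LSMD)/√(1/n_dose + 1/n_placebo), with the model degrees of freedom.
- Compute the repeated CI directly from the stage-wise LSMD, its SE and df. This matches what 8.4.3 already does with the log-hazard ratio, and avoids forcing two doses with different SEs through one common SD.

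State the LS-mean weighting over region and antibody status as well, since it affects the arm LS means that are reported.

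Add a check that the stage-wise p-values reproduced by RPACT equal the MMRM p-values for each dose. Do not require the CI to exclude zero exactly when the closed test rejects. Instead, state which multiplicity adjustment the interval uses, so that any difference from the closed test can be explained.

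The cost is a few sentences in the SAP and about a line of code. No design, data collection or sample size changes.

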8.2.3 Sensitivity analyses of the primary efficacy endpoint

8.2.3.1 Sensitivity Analysis #1

The first sensitivity analysis will be performed based on the FAS using the hypothetical & treatment policy strategy. The method to handle missing MG-ADL scores (including missing data after the intercurrent events) is specified in [Section 4.2.1](#).

The same stage-wise analysis approach as primary analysis ([Section 8.2.2](#)) will be repeated.

8.2.3.2 Sensitivity Analysis #2

The second sensitivity analysis will be performed based on the RS under the hypothetical & treatment policy strategy. A J2R approach using Multiple Imputation (MI) method under missing not at random (MNAR) assumption will be used to handle any missing MG-ADL scores (including missing data after the intercurrent events). Missing data will be imputed based on the placebo group distribution, irrespective of individual treatment assignment.

The following is a summary of the imputation method.

100 imputed datasets (m) will be created using monotone linear regression imputation methods which will impute the study participants' missing post-baseline scores at each of the scheduled visits in the study (i.e., Days 1, 8, 15, 22, 29, 36 and 43). If the missing data does not follow a monotonic pattern, a sequential approach to imputing the data to produce a monotone missing data pattern will be applied using the MCMC impute=monotone option in PROC MI (SAS System). Then the monotone linear regression imputation methods will be applied.

The MI method allows for a pattern-mixture model approach assuming the data are MNAR. The MNAR option in PROC MI (SAS system) will be used to impute the placebo distribution as described in Yuan (2014).

Each of the imputed datasets will be analyzed via the specified MMRM model (see [Section 8.2.2](#)). The treatment effects and standard errors from LSMs and LSMDs will be combined across the 100 imputed datasets to produce an overall LSMs and LSMDs with associated p-value and 97.5 % CI using SAS PROC MIANALYZE.

The following variables will be included in the imputation model:

- o Baseline MG-ADL Score (continuous variable)
- o MG-ADL Score at Days 8, 15, 22, 29, 36 and 43 (continuous variable)

Note: if the MI model does not converge or produce estimates (e.g., due to over-specification) the set of imputation variables may be modified.

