8.1 Handling of intercurrent events

The main intercurrent events (ICEs) of interest are:

- ICE1 – The use of rescue therapy prior to Day 43 (Visit 10)
- ICE2 – Permanent treatment discontinuation (or withdrawal from study) due to TEAEs

Two additional types of ICEs will be included to account for data affected by the COVID-19 pandemic as follows:

- ICE3 – Treatment discontinuation due to suspected/confirmed COVID-19 infection (“Confirmed COVID-19” or “Suspected COVID-19” as the relationship to COVID-19 in the COVID-19 Impact eCRF)
- ICE4 – Treatment discontinuation due to non-COVID-19 infection related issues (“General circumstances around COVID-19 pandemic without infection” or “other” as the relationship to COVID-19 in the COVID-19 Impact eCRF)

The number and percentage of study participants with each intercurrent event will be summarized by treatment group and RLZ total.

The strategies to handle ICEs are summarized as below:

Strategies	Description
Hypothetical & treatment policy strategy	
If study participants experience ICE1, data at and after the point of the ICE for the purpose of analysis will be treated as missing and imputed under proposed method per Section 4.2.1.
 
For participants experiencing ICE2-4, data in the Treatment Period from Baseline to Day 43 will be used regardless of whether any ICEs occurred, missing data will be imputed per Section 4.2.1.
 
For participants who permanently discontinue treatment or withdraw from the study during Treatment Period and who continue into the Observation Period, the observation phase data (collected bi-weekly) will be mapped to the nearest visit for primary analysis where treatment windows will be utilized for the mapping.

Treatment policy strategy	The data in the Treatment Period from Baseline to Day 43 will be used regardless of whether any intercurrent events occurred.
Composite strategy	The occurrence of any intercurrent events above will be handled by evaluating the corresponding study participants as treatment failures and imputed with a worst score (continuous) or non-responder (binary).
COVID-19 Hypothetical strategy	
If participant experience ICE1 and/or ICE2, then data at and after the point of the intercurrent event for the purpose of analysis will be treated as missing.
 
Additionally, participant experience ICE3, ICE4 or those that have visits in treatment period affected (e.g. visit performed by video call) will be completely removed from analysis.

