Dosing instructions:	
█ doses of rozanolixizumab at █ (equivalent to approximately █):
 
Bodyweight <50kg: dose to be administered █
 
Bodyweight ≥50kg and <70kg: dose to be administered █
 
Bodyweight ≥70kg and <100kg: dose to be administered █
 
Bodyweight ≥100kg: dose to be administered █
	
█ doses of rozanolixizumab at █ (equivalent to approximately █):
 
Bodyweight <50kg: dose to be administered █
 
Bodyweight ≥50kg and <70kg: dose to be administered █
 
Bodyweight ≥70kg and <100kg: dose to be administered █
 
Bodyweight ≥100kg: dose to be administered █
	
█ doses of placebo at █

Packaging and Labeling	Rozanolixizumab and matching placebo are manufactured, packaged, and labeled according to Good Manufacturing Practice guidelines and applicable laws or regulations.		

2. **Population:** study participants with generalized MG who comply with the inclusion/exclusion criteria specified in Section 5 in the study protocol
3. **Endpoint:** please refer to Section 2.2.1.1 for details.
4. **Intercurrent Events (ICEs):** See Section 4.2.1.
5. **Population Level Summary (PLS):** See table below.

Table 8-2: Intercurrent Events and Population Level Summary by Statistical Category

Statistical Category	Intercurrent Event Strategy	Population Level Summary
Primary	The ICEs are detailed in Section 8.1 . A hypothetical & treatment policy strategy will be used to handle the ICEs.	Difference in mean change from Baseline (LSMD from CfB MMRM) to Day 43 (Visit 10) in the MG-ADL score for study participants receiving rozanolixizumab versus placebo, using the RS.
Sensitivity	Hypothetical & treatment policy strategy , same as for the primary analysis	Difference in mean change from Baseline (LSMD from CfB MMRM) to Day 43 (Visit 10) in the MG-ADL score for study participants receiving rozanolixizumab versus placebo, using the FAS.
Sensitivity	Hypothetical & treatment policy strategy , same as for the primary analysis	Difference in mean change from Baseline (LSMD from CfB MMRM) to Day 43 (Visit 10) in the MG-ADL score for study participants receiving rozanolixizumab versus placebo, using the RS. A Jump-to-reference multiple imputation approach will be utilised to assess the validity of the MAR assumption. Missing data across all treatment groups will be imputed using the placebo distribution.

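### SAP 8.2.3.2 is labelled jump-to-reference, but the procedure it describes is copy-reference, a less severe check than the label states

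*SAP*

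**What the plan says.** SAP 4.2.1, 8.2, 8.2.3.2 and Tables 8-2 and 8-3 all label this analysis J2R or jump-to-reference, as does Table 9-1 of the protocol. SAP Table 8-2 gives its purpose: "A Jump-to-reference multiple imputation approach will be utilised to assess the validity of the MAR assumption". Section 8.2.3.2 opens in the same terms: "A J2R approach using Multiple Imputation (MI) method under missing not at random (MNAR) assumption will be used to handle any missing MG-ADL scores".

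The section then sets out the method:

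- Engine: "100 imputed datasets (m) will be created using monotone linear regression imputation methods", one scheduled visit after another.
- Reference: "The MNAR option in PROC MI (SAS system) will be used to impute the placebo distribution", for every arm: "Missing data will be imputed based on the placebo group distribution, irrespective of individual treatment assignment".
- Imputation variables: the participant's own baseline score and "MG-ADL Score at Days 8, 15, 22, 29, 36 and 43 (continuous variable". No arm-mean profile and no centring step is listed.

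Under the primary strategy in SAP 8.1, once rescue therapy is used, "data at and after the point of the ICE for the purpose of analysis will be treated as missing". Scores from before rescue are kept and so are available as predictors. SAP 8.3.2 to 8.3.6 apply the same imputation to MG-C, QMG and the three MG Symptoms PRO scores.

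**The concern.** Both methods use placebo data to fill in missing active-arm values, but they treat the earlier scores differently. In jump-to-reference, the mean moves to placebo once data become missing, and only the participant's deviation from their own arm's mean is carried forward. In copy-reference, the participant is treated as a placebo participant throughout, so benefit already gained on the drug counts as a favourable deviation from placebo and persists in the imputed value. The listed procedure does the second.

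The stake is what may be claimed from the result. Sensitivity analyses 1, 3 and 4 use maximum likelihood under MAR, so this is the only departure from MAR that keeps the primary estimand and the MMRM. A report of robustness under jump-to-reference would claim a full loss of effect after dropout that was not imposed. The wording also lets two programmers, one following the label and one the variable list, reach different estimates.

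**Working it through.** **Anchor.** The plan gives no figure for this analysis. SAP 2.4 sets the scale: effect 1.5 to 2.0 points, SD 3.5 to 4. A 100,000-run simulation of the two-stage design with known-SD z-tests gave power 0.950 for scenario 7 of SAP Table 2-1 (both doses 2.0, SD 3.5), against 0.943 stated. Scenarios 1, 4, 5 and 14 gave 0.020, 0.763, 0.874 and 0.881, against 0.020, 0.750, 0.864 and 0.871. Effect 2.0 and SD 3.5 are used below.

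**Formulas.** Let y be an active-arm participant's scores up to the last visit seen, P and A the placebo and active means at those visits, P43 the placebo mean at Day 43, and B the placebo regression coefficients of Day 43 on those visits. The expected imputed Day 43 value is:

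- as written: P43 + B(y − P)
- jump-to-reference: P43 + B(y − A)

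The difference is B(A − P). It does not depend on the individual's own scores. Share of the Day 43 effect kept = B(A − P) / (effect at Day 43). Under jump-to-reference this share is 0.

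**Assumptions (none is in the documents).** Equal SDs. Compound symmetry or AR(1), correlation 0.5, 0.7 or 0.85. Effect at baseline and Days 8 to 43 as a fraction of the Day 43 effect: constant (0, then 1 throughout), linear (0, 1/6, … 1) or fast (0, 0.4, 0.7, 0.85, 0.95, 1, 1).

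**Hand checks.**

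- AR(1) 0.5, linear, last seen Day 8: 0.5^5 × 1/6 = 0.005, about 1%.
- Compound symmetry 0.5, constant, last seen Day 8: each coefficient is 0.5/1.5 = 1/3 and baseline carries no effect, so 1/3 × 0 + 1/3 × 1 = 33%.
- AR(1) 0.85, linear, last seen Day 29: 0.85² × 4/6 = 48%.
- AR(1) 0.85, fast, last seen Day 36: 0.85 × 1 = 85%.

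**Share kept, averaged over last visits Day 8 to Day 36, for correlations 0.5 to 0.85.**

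| Onset | Compound symmetry | AR(1) |
|---|---|---|
| Constant | 56–68% | 19–63% |
| Fast | 37–44% | 18–52% |
| Linear | 20–24% | 13–35% |

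**Effect on the overall estimate.** With fraction m missing and average share s kept, the estimate is 2.0 × [1 − m(1 − s)]. For jump-to-reference s = 0, which gives 2.0 × (1 − m). The written procedure was also run directly (40,000 per arm; fast onset; compound symmetry 0.5 and 0.7, AR(1) 0.85). Sizes of the estimated difference:

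| Missing | Jump-to-reference, 2.0(1 − m) | As written, direct run | Shift towards MAR, direct run |
|---|---|---|---|
| 5% | 1.9 | 1.91–1.97 | 0.04–0.05 |
| 10% | 1.8 | 1.86–1.92 | 0.07–0.10 |
| 20% | 1.6 | 1.74–1.80 | 0.16–0.20 |
| 30% | 1.4 | 1.59–1.74 | 0.21–0.32 |

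The shift is taken against jump-to-reference run on the same simulated data (for example 1.86 against 1.79 at 10% missing, compound symmetry 0.5). MAR gives 2.0 throughout.

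The direct run covers fast onset only. Across the averages above (s from 0.13 to 0.68) the shift is 2.0 × m × s. At 10% missing that is 2.0 × 0.10 × 0.13 = 0.03 to 2.0 × 0.10 × 0.68 = 0.14. At 20% it is 0.05 to 0.27.

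**The case against.** The strongest reply is that section 8.2.3.2 calls its own text a summary, relies on a cited software paper, and allows the variable set to change. Its list also omits treatment, which the program must use to identify placebo. And jump-to-reference conditions on earlier scores too, as residuals, so listing those scores does not by itself separate the methods. It stands that the program is not visible, and a reader should not infer that the code is known to be wrong. But the specification contains no centring on own-arm means, and the permitted change to the variables is for a model that fails to converge or give estimates. Neither supplies the missing step.

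Three stronger readings are tempting, and the documents do not support them.

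- **That most of the drug effect survives imputation.** No visit correlation, onset curve or missing-data rate is given. Early dropout with slow onset keeps almost nothing; a large share needs late dropout, early onset or high correlation.
- **That the plan has no other MNAR check.** The trimmed-mean analysis in SAP 8.2.4.1 assumes MNAR, assigns the worst score, and is repeated for the five continuous secondary endpoints. It is harsher than jump-to-reference. It uses a composite strategy and ANCOVA, so it answers a different question and does not replace this check.
- **That the sentence on the placebo distribution is itself wrong.** It fits either method. The mismatch is between the label and the listed model.

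The objection that the practical effect may be small also stands. Under SAP 8.1 only rescue sets observed scores to missing in the primary strategy. Data after the other intercurrent events are used, and Observation Period scores are mapped in for those who stop treatment. The analysis is also outside the confirmatory testing procedure in SAP 4.6.

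**Conclusion.** The point holds as a mismatch between name and method. As written, the analysis is copy-reference. With positive within-person correlation and any drug benefit before data become missing, it is less severe than jump-to-reference, and the error favours the drug. Direction follows from the specification; size rests on the assumptions stated.

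At 5 to 10% missing the shift is small, about 0.04 to 0.10 points on a true effect of 2.0 in the direct run. At 20 to 30% it is 0.16 to 0.32. SAP 2.4 treats a difference above 1.5 as clinically meaningful. At 10 and 20% missing both methods stay above that value. At 30%, jump-to-reference gives 1.4 while the written procedure gives 1.59 to 1.74, but nothing in the documents indicates that so much will be missing.

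The figures use the MG-ADL visit schedule. The MG Symptoms PRO is collected at fewer visits, so for those endpoints only the direction carries over. The primary analysis and its conclusion are unaffected.

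**What to change.** Preferred: specify the method that both documents name. In SAP 8.2.3.2, state that active-arm missing values are drawn around the placebo mean profile from the first missing visit, conditioning on residuals of the observed scores from the participant's own arm means, fitted within each stage. Carry this through to SAP 8.3.2 to 8.3.6.

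Minimum: rename the analysis copy-reference in SAP 4.2.1, 8.2, 8.2.3.2 and Tables 8-2 and 8-3, record the departure from protocol Table 9-1 in SAP 3.9, and do not report the result as robustness under jump-to-reference.

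The cost is SAP wording, a modest change to the imputation program for the preferred option, and a slightly less favourable sensitivity estimate.
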